3. PURPOSE OF THE STATISTICAL ANALYSIS PLAN

The purpose of this SAP is to document technical and detailed specifications for the final analysis of data collected from protocol HGT-HIT-094 Amendment 5 and to support completion of the clinical study report for submission to regulatory authorities.

4. SUMMARY OF CLINICAL TRIAL FEATURES

4.1 General Description

Study Design	
The pivotal study HGT-HIT-094 is a Phase II/III randomized, controlled, 2-arm, open-label, assessor-blinded, multicenter study to determine the effect on clinical parameters of neurodevelopmental status following monthly IT administration of idursulfase-IT 10 mg for 12 months in pediatric patients aged 3 to <18 years with Hunter syndrome and early cognitive impairment who have previously received and tolerated a minimum of 4 months of IV therapy with Elaprase (0.5 mg weekly). All patients continue to receive Elaprase therapy as standard of care throughout the study.
 
The pivotal study design is “no IT treatment-controlled”. At least 48 patients are assigned randomly in a 2:1 ratio to IT treatment or no IT treatment arms.
 
The separate substudy is open label with a single idursulfase-IT treatment arm. Patients will receive 12 monthly doses of idursulfase-IT. Patients in the substudy are <3 years old with Hunter syndrome and early cognitive impairment who have previously received and tolerated a minimum of 4 months of therapy with Elaprase. There is no target enrollment number for this substudy. The patients’ doses will be given based on reference brain weight as follows to account for brain weight development:
 
• up to 8 month at dosing: 5 mg• >8 months to 30 months at dosing: 7.5 mg• >30 months to 3 years at dosing: 10 mg 
Those patients in the substudy and those randomized to the IT treatment arm in the pivotal study will undergo surgical implantation of the SOPH-A-PORT[®] Mini S IDDD followed by a post-operative recovery period of at least 14 days prior to the first IT administration of idursulfase-IT. Treated patients in the pivotal study and the substudy will then receive 12 monthly IT injections of idursulfase-IT corresponding to a treatment and assessment interval of 13 months from randomization to the end-of-study (EOS) evaluations. Likewise, patients randomized to the no IT treatment arm will be assessed over 13 months after randomization.
 
The SOPH-A-PORT[®] Mini S IDDD is used to obtain cerebrospinal fluid (CSF) samples and to deliver all IT injections of idursulfase-IT. If the IDDD appears to be non-functional, or if its use is precluded on a scheduled day of dosing, site personnel will refer to the IDDD Manual, which provides details on the investigation and management of any IDDD-related issues. If the IT space is not accessible via the IDDD, lumbar puncture may be utilized under defined circumstances for administration of idursulfase-IT or to obtain a CSF sample.

--------------	---

Study Product	idursulfase for intrathecal use (idursulfase-IT [HGT-2310])
Intrathecal drug delivery device	SOPH-A-PORT [®] Mini S, Implantable Access Port, Spinal, Mini Unattached, with Guidewire (SOPH-A-PORT [®] Mini S)
Study Objectives	
Primary Objective
 
 • To determine the effect of the treatment regimen in pediatric patients with Hunter syndrome and early cognitive impairment on the General Conceptual Ability (GCA) score as measured by the DAS-II, in conjunction with Elaprase therapy 
Secondary Objectives
 
The key secondary objective of this study is:
 
 • To determine the effect of the treatment regimen in pediatric patients with Hunter syndrome and early cognitive impairment on the Adaptive Behavior Composite (ABC) score as measured by the VABS-II, in conjunction with Elaprase therapy 
The secondary objectives of this study are:
 
 • To determine the effect of the treatment regimen in pediatric patients with Hunter syndrome and early cognitive impairment, in conjunction with Elaprase therapy, on: 
 ○ Cognitive function as measured by the cluster areas and subtests of the DAS-II ○ Adaptive behavior as measured by the domains and subdomains of the VABS-II 
Safety Objectives
 
 • To determine the effect of the treatment regimen on safety as assessed by adverse events, clinical laboratory testing, physical and neurological examination findings, vital signs, and electrocardiogram (ECG) results • To evaluate the anti-idursulfase antibody response in serum and cerebrospinal fluid (CSF) during the treatment regimen 
SOPH-A-PORT[®] Mini S Device Objectives
 
 • To determine the safety and performance of the SOPH-A-PORT[®] Mini S device 
Pharmacokinetic and Pharmacodynamic Objectives
 
 • To evaluate the concentration of idursulfase and determine pharmacokinetic (PK) parameters in serum after IT administration • To evaluate the concentration of idursulfase in CSF prior to each monthly administration of idursulfase-IT • To determine the effect of the treatment regimen on the concentration of

	
glycosaminoglycan (GAG) in CSF
 
Health Status Objective
 
 To evaluate health status as measured by the EQ-5D instrument 
Substudy Objective
 
 To examine the effect of the treatment regimen on safety and efficacy measures in pediatric patients with Hunter syndrome and early cognitive impairment who are below 3 years of age

Study Endpoints
	
Primary efficacy endpoint
 
 Change from baseline in the GCA standard score after 12 months of treatment at Visit Week 52, as obtained by DAS-II testing 
Key secondary efficacy endpoint
 
 Change from baseline in the ABC standard score after 12 months of treatment at Visit Week 52, as obtained by VABS-II testing 
Secondary efficacy endpoints
 
 Change from baseline to Visit Weeks 16, 28, and 40 in the GCA standard score as obtained by DAS-II testing Change from baseline to Visit Weeks 16, 28, and 40 in the ABC standard score as obtained by VABS-II testing Change from baseline to Visit Weeks 16, 28, 40, and 52 in standard scores in cluster areas of the DAS-II: Verbal, Nonverbal, Spatial, and Special Nonverbal Composite (SNC) Change from baseline to Visit Weeks 16, 28, 40, and 52 in the standard scores of the VABS-II domains: Communication, Daily Living Skills, Socialization, and Motor Skills Change from baseline to Visit Weeks 16, 28, 40, and 52 in the age equivalents, developmental quotients (DQ), and T scores for the subtests of the DAS-II (Verbal Comprehension, Picture Similarities, Naming Vocabulary, Pattern Construction, Matrices, and Copying for the DAS-II/Early Years, and Recall of Designs, Word Definitions, Pattern Construction, Matrices, Verbal Similarities, and Sequential and Quantitative Reasoning for the DAS-II/School Years) Change from baseline to Visit Weeks 16, 28, 40, and 52 in the age equivalents, DQ and v-scale scores of the VABS-II subdomains: Communication (Receptive, Expressive, Written), Daily Living Skills (Personal, Domestic, Community), Socialization (Interpersonal Relationships, Play and Leisure Time, Coping Skills), Motor Skills (Gross, Fine) Change from baseline to Visit Weeks 16, 28, 40, and 52 in v-scale scores and the observed maladaptive levels of the VABS-II Maladaptive

	
Behavior Index and its subscales (Internalizing, Externalizing)
 
Exploratory efficacy endpoint
 
 • Slope estimate from the linear regression of GCA scores over time for each subject 
Additional efficacy endpoint for substudy only
 
 • Observed value in raw score, age equivalents versus chronological age, as well as DQ, composite score and percentile for the three scales of the BSID-III (Motor [Fine, Gross], Language [Receptive, Expressive], Cognitive) for substudy only 
Pharmacokinetic and Pharmacodynamic endpoints
 
 • Serum concentration of idursulfase and serum PK parameters after IT administration • CSF concentration of idursulfase prior to each monthly IT administration • Change from baseline in the concentration of GAG in CSF 
Safety Assessments
 
Safety will be assessed during the study by collection of adverse events (by type, severity, and relationship to treatment [idursulfase-IT, the IDDD, device surgical procedure, or IT administration process] and IV Elaprase infusion), changes in clinical laboratory testing (serum chemistry, hematology, urinalysis), physical and neurological examination, vital signs, 12-lead ECG, CSF laboratory parameters (chemistries, cell counts), anti-idursulfase antibodies in CSF and serum, and determination of antibodies having enzyme neutralizing activity.
 
SOPH-A-PORT[®] Mini S Device Assessments
 
The SOPH-A-PORT Mini S device will be evaluated using assessments of device implantation, device function, device longevity and adverse events associated with the implant surgery or device. Those data will be collected on the patient's electronic case report form (eCRF) from the time of initial implantation and continue throughout the study as long as the SOPH-A-PORT[®] Mini S remains implanted.
 
Health Status Assessment
 
Health status dimensions as obtained by the EQ-5D questionnaire: mobility, self-care, usual activities, pain/discomfort, and anxiety/depression.

Number of Subjects	
Pivotal study
 
 • 48 male patients (32 IT treated and 16 No IT treatment) are planned.

	
Substudy
 
 • There is no pre-specified number of patients planned. The enrollment will conclude when enrollment of patients in the pivotal study closes.

Treatment and Study Duration
	
Patients in the IT treatment arm of the pivotal study will be assessed according to the following schedule:
 
 • Screening (Visit Weeks -4 to -1 [Day -28 to Day -1]) • Randomization (Visit Week 0 [Day 0]) • Pre-surgery, Surgery, Follow-up, and Post-operative Recovery (Visit Week 2 [+7 days]) • Treatment and Assessments(Visit Week 4 through Week 48 [±7 days]) • End of study (EOS, Visit Week 52 [±7 days]) • Follow-up (telephone contact) 7 (±2) days from the Visit Week 52 (or EOS) 
Patients in the no IT treatment arm of the pivotal study will be assessed according to the following schedule:
 
 • Screening (Visit Weeks -4 to -1 [Day -28 to Day -1]) • Randomization (Visit Week 0 [Day 0]) • Telephone contact (Week 2 [+7 days]) • Assessments (Visit Week 4 through Week 48 [±7 days]) • End of study (EOS, Visit Week 52 [±7 days]) • Follow-up (telephone contact) 7 (±2) days from the Visit Week 52 (or EOS) 
The separate substudy is open-label and single arm. Patients who meet all entry criteria for participation in the substudy will be considered enrolled on Day 0. Thereafter, patients who are enrolled in the separate substudy will follow a similar schedule of treatment and assessments as idursulfase-IT-treated patients in the pivotal study.
 
Patients in the substudy will be assessed according to the following schedule:
 
 • Screening (Visit Weeks -4 to -1 [Day -28 to Day -1]) • Enrollment (Week 0 [Day 0]) • Pre-surgery, Surgery, Follow-up, and Post-operative Recovery (Visit Week 2 [+7 days]) • Treatment and Assessments(Visit Week 4 through Week 48 [±7 days]) • End of study (EOS, Visit Week 52 [±7 days]) • Follow-up (telephone contact) 7 (±2) days from the Visit Week 52 (or EOS) 
The planned overall duration of each patient’s participation in the study is approximately 14 to 15 months from Screening to the last scheduled contact.

Randomization and
	
A centralized randomization procedure is utilized to randomize patients in a 2:1

Blinding	
allocation ratio to study arms (32 IT treated and 16 No IT treatment patients). The randomization is stratified by baseline GCA score (≤ 70 and > 70).
 
HGT-HIT-094 is an open label study. Single and double blinding of patients, their families, and the Principal Investigator is not possible due to the absence of a sham device, sham injections, or placebo. The assessors responsible for the DAS-II and VABS-II evaluations will not be informed of patients' randomization assignments. The families will be instructed not to share this information with the assessors.
 
Different assessors will be responsible for administration of the DAS-II and VABS-II. All assessments will be administered by qualified study personnel. The DAS-II will be administered by a trained practitioner. Shire will have no access to unblinded DAS-II and VABS-II data during the study.
 
The separate substudy is open label and non-randomized, with a single idursulfase-IT treated arm.

----------	--

4.2 Determination of Sample Size/Randomization

Based on study HGT-HIT-050/045 Phase I/II data, the observed decline in mean General Conceptual Ability (GCA) standard score (SS) in No IT treatment patients was estimated to be 13.7 points with a standard deviation of 9.4 after 12 months. For the sample size calculation, we conservatively assumed an approximately 1 point per month rate of decline in the No IT treatment arm, so that the theoretical decline would be 13 points from baseline (Screening Visit) to Visit Week 52 (~ 13 months). As up to 2 months may elapse between the screening assessment and the start of idursulfase-IT treatment, a mean decline of 2 points at end of study would be expected if idursulfase was effective in stabilizing the decline. Therefore, in such a case, the mean projected treatment difference at Visit Week 52 would be 11 points, which is considered a clinically meaningful treatment difference.

Using a 2:1 allocation ratio, a sample size of 48 randomized patients (about 32 IT treated patients and 16 no IT treatment patients) will yield 80% power to detect a clinically meaningful mean treatment difference of 11 points in the primary endpoint, GCA change from baseline to Visit Week 52. This calculation further assumes a common standard deviation for the change from baseline of 11.6 points, a type-I error rate of 0.05 for a two-sided two-sample t-test, with approximately up to 10% missing an assessment at Visit Week 52. Given this sample size, and conditional on rejection of the null hypothesis for the primary endpoint, the power would be 80% to detect a clinically meaningful mean difference of 10 points in the key secondary endpoint, change from baseline in ABC standard score at Visit Week 52, assuming a standard deviation for the change from baseline of 10.5 points for a two-sided two-sample t-test with a significance level of 5% and 10% missing an assessment at Visit Week 52.

The variance estimate for this sample size was determined based on a blinded variability assessment (BVA) performed as specified in the prior protocol version (Amendment 3); refer to

[Appendix 5](#) of the protocol Amendment 5 for details. Given that uncertainty around this variability estimate remained, a second BVA using the same approach as specified in [Appendix 5](#) of the protocol Amendment 5 was performed to confirm the estimate after approximately 27 patients completed the Week 52 primary endpoint assessment. Based on this second blinded assessment, the sample size was set to 48 patients while maintaining the 2:1 allocation ratio. As there was no treatment comparison involved, no inflation of the type I error from this procedure was expected, and no adjustment to the significance levels for the final analysis was necessary.

Patients will be randomized (open-label, assessor-blinded) in a 2:1 allocation ratio between the idursulfase-IT treatment regimen and no IT treatment groups. Although this is a multi-center study, the randomization will not be stratified by center. The baseline GCA score (at Screening Visit) is expected to be a key prognostic factor. Therefore, the randomization will be stratified according to baseline GCA score: ≤ 70 versus > 70 . The randomization schedule will be generated and administered centrally by Pharmaceutical Product Development, LLC (PPD), independent of the sponsor's project team. There is no replacement of patients who do not complete the study.

In a separate substudy, additional patients with cognitive impairment may be enrolled who are below the age of 3 years at the time of informed consent. All patients meeting eligibility criteria for the substudy will be enrolled until enrollment for the pivotal study is completed. There is no target sample size. Such patients are ineligible for the pivotal trial and will not be randomized, but will receive idursulfase-IT treatment monthly.

5. EFFICACY AND SAFETY ENDPOINTS

5.1 Schedule of Evaluations

The detailed schedule of evaluations can be found in the HGT-HIT-094 protocol (Amendment 5).

5.2 Primary Efficacy Endpoint

The primary efficacy endpoint is described above in Section 4.1.

5.3 Secondary Efficacy Endpoints

5.3.1 Key Secondary Efficacy Endpoint

The key secondary efficacy endpoint is described above in Section 4.1.

5.3.2 Other Secondary Efficacy Endpoints

The other secondary efficacy endpoints are described above in Section 4.1.

5.4 Exploratory Efficacy Endpoint

The exploratory endpoint is described above in Sections 4.1.

5.5 Pharmacokinetic and Pharmacodynamics Endpoints

The PK and PD endpoints are described above in Section 4.1.

5.6 Safety Assessments

The safety assessments are described above in Section 4.1.

5.7 SOPH-A-PORT® Mini S Device Assessments

The device assessments are described above in Section 4.1.

5.8 Health Status Assessments

The health status assessments are described above in Section 4.1.

5.9 Cerebrospinal Fluid Assessments

Cerebrospinal fluid will be obtained from patients in the treated arm of the pivotal study and in the substudy at Screening Visit (by lumbar puncture and under general anesthesia), during surgical implantation of the IDDD, prior to each intrathecal injection of investigational product, and at the Week 52/EOS visit. Patients in the no treatment arm of the pivotal study will undergo

lumbar puncture (under general anesthesia) to obtain CSF samples at Screening and the Week 52/EOS visits.

6. STATISTICAL ANALYSIS

6.1 General Methodology

All statistical analyses will be performed by the Biostatistics and Statistical Programming department at Shire unless otherwise specified, using SAS[®] software version 9.3 or higher (SAS Institute, Cary, N.C., USA).

Continuous variables will be summarized using descriptive statistics (N, mean, standard deviation, minimum, median, and maximum). Categorical variables will be summarized using the number and percentage of patients in each category. Data will be summarized with respect to patient disposition, demographic and baseline characteristics and concomitant medication use. The efficacy endpoints, safety assessments and other outcome results for each treatment group will be summarized descriptively unless otherwise indicated. In addition, statistical model estimates of least squares means, treatment differences, p-values and 95% confidence intervals for least squares mean treatment differences will also be provided where relevant for efficacy endpoints. The fit of linear models will be assessed using residual plots and/or other diagnostic plots as appropriate. All the statistical tests will be 2-sided and performed at the 0.05 level of significance unless stated otherwise. Baseline is defined as the value at Screening Visit for all parameters, unless specified otherwise. The planned analyses described below in this SAP pertain to the pivotal study data.

The separate substudy is an open-label, single arm study. Data from patients participating in this separate substudy will be analyzed separately. Since the number of patients enrolled in the substudy is expected to be low, their safety and efficacy data will not be summarized, but the corresponding data as described for the pivotal study will be listed. The listing format would be the same as that for the pivotal study where relevant.

6.2 Analysis Populations

For the pivotal study, all efficacy and pharmacodynamic data analyses will be performed according to treatment assigned using the Intent-to-Treat (ITT) Population, which is defined as all randomized patients.

All safety data analyses will be performed according to treatment received using the Safety Population, which is defined as all randomized patients with any post-randomization safety assessments. IDDD and procedure related analyses will be conducted in the set of patients in the Safety Population who had the device implant procedure performed.

For the substudy, analyses will be performed on the Substudy Population, defined as all patients enrolled and treated with study drug in the substudy.

All pharmacokinetic data analyses will be performed using the Pharmacokinetic (PK) Population. The PK Population is defined as all patients who receive study drug and participate

in the scheduled pharmacokinetic studies, and for whom at least 1 post-dose PK blood sample was collected.

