8.3.1.4 Post-op Recovery

Surgical implantation of the IDDD will be followed by a post-operative recovery period of at least 14 days prior to the first IT administration of idursulfase-IT.

8.3.2 Patients in the IT Treatment Group of the Pivotal Study and All Patients in the Substudy: IT Dosing (Weeks 4, 8, 12, 16, 20, 24, 28, 32, 36, 40, 44, 48 [\pm 7 days])

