10.4 Population Description and Exposure

10.4.1 Analysis Populations

For the pivotal trial, all efficacy data analyses will be performed using the Intent-to-Treat (ITT) Population, which is defined as all randomized patients.

All safety data analyses will be performed according to treatment received using the Safety Population, which is defined as all randomized patients with any post-randomization safety assessments. IDDD and procedure related analyses will be conducted in the set of patients in the Safety Population who had the device implant procedure performed.

For the substudy, analyses will be performed on the Substudy Population, defined as all patients enrolled and treated with study drug in the substudy.

All pharmacokinetic data analyses will be performed using the Pharmacokinetic Population. The Pharmacokinetic Population is defined as all patients for whom the primary pharmacokinetic data are considered sufficient and interpretable.

The planned analyses described below pertain to the pivotal study data. Similar descriptive summaries or listings as appropriate will be provided for the substudy data.

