10.7.2 IDDD and Procedure Related Adverse Events

IDDD and procedure related adverse events will be summarized within SOC by preferred term. Separate tabulations will be provided for adverse events related to the IDDD, device surgical procedure, and IT-administration process. An overall summary of adverse events related to the IT treatment regimen (ie, related to one or more of the following: study drug, IDDD, device surgical procedure, and IT-administration process) will also be presented. IDDD and procedure related events will be analyzed in the set of treated patients in the Safety Population with the device implanted.

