The AE categories 1-7 will be presented by each treatment group for patients in the Safety Population, while the AE categories 8-12 will be presented by each treatment group for patients in the Safety Population who received idursulfase-IT. IT administration process-related AEs will be summarized by IT administration method (LP or IDDD) as well. The AE categories 10-11 will be presented for patients in the Safety Population with the device implanted. The number and proportion of patients, and the number of corresponding AEs will be summarized in overall summary tables. In addition, the number and percentage of patients having any treatment-emergent AE within the AE categories 2, 5, 7-12 and the number of corresponding AEs will be displayed by MedDRA system organ class (SOC), preferred term (PT) and treatment group. The most common treatment-emergent AEs which happened in >10% patients in either treatment group will also be summarized by SOC and PT. The most common non-serious treatment-emergent AEs which happened in >5% patients in either treatment group will also be summarized by SOC and PT.

The number and percentage of patients having any treatment-emergent AE, and the number of corresponding AEs will be summarized by MedDRA SOC, PT and severity.

The number and percentage of patients having any treatment-emergent AE, and the number of corresponding AEs will be summarized by relationship to IV Elaprase, idursulfase-IT, and at least one IT treatment regimen, and summarized by MedDRA SOC and PT.

Furthermore, listings of all the AEs of categories 3-6 will be provided if applicable.

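### The Substudy Population and the summary of IT-regimen-related adverse events both require a dose of idursulfase-IT, although device surgery belongs to the regimen and normally comes first

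*SAP*

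**What the plan says.** **Order of events.** Protocol 8.3.1.4: "Surgical implantation of the IDDD will be followed by a post-operative recovery period of at least 14 days" before the first IT dose. SAP 6.8.1 opens the treatment-emergent window in the IT arm at the first implantation or the first dose, whichever comes earlier.

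**Pivotal study.** SAP 6.2 uses the "Safety Population, which is defined as all randomized patients with any post-randomization safety assessments", which has no dosing condition. Within it, SAP 6.8.1 sets three rules:

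- "The AE categories 1-7 will be presented by each treatment group for patients in the Safety Population". These categories include deaths, serious events, severe events and discontinuations due to adverse events.
- "the AE categories 8-12 will be presented by each treatment group for patients in the Safety Population who received idursulfase-IT". Category 9 is relatedness to any part of the IT regimen: drug, device, device surgery or administration process.
- "The AE categories 10-11 will be presented for patients in the Safety Population with the device implanted". These two categories are surgery-related and device-related events.

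**Protocol wording for device and procedure events.** Section 10.4.1: "IDDD and procedure related analyses will be conducted in the set of patients in the Safety Population who had the device implant procedure performed"; SAP 6.2 says the same. Section 10.7.2: "IDDD and procedure related events will be analyzed in the set of treated patients in the Safety Population with the device implanted".

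**Substudy.** The only set defined, in SAP 6.2 and Protocol 10.4.1, is the "Substudy Population, defined as all patients enrolled and treated with study drug in the substudy". SAP 6.1, 6.7 and 6.8 provide listings for the substudy, not summaries.

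**The concern.** The sponsor treats implantation as part of the regimen: regimen-relatedness includes it, and the treatment-emergent clock can start with it. A set that also requires a dose can lose a patient because of what happened at surgery. If implantation leads to a complication after which the patient is withdrawn before the first dose, the event that prevented dosing is also what removes him from the set.

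Two outputs are exposed. The first is the substudy safety listing, in children under 3 for whom safety is a stated objective (Protocol 2.7). The second is category 9, the summary meant to show the total harm attributable to the regimen. Separately, the programmer of categories 10-11 has several descriptions of the denominator, and they do not all select the same patients.

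**Working it through.** The plan states no figure for this point, so there is none to reproduce. The check is to follow one hypothetical patient, implanted but never dosed, through each definition.

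| Output | Set stated | Is he in it? |
|---|---|---|
| Pivotal Safety Population (SAP 6.2) | Randomized, any post-randomization safety assessment | Yes |
| Categories 1-7 (SAP 6.8.1) | Full Safety Population | Yes |
| Category 9 and its SOC/PT table (SAP 6.8.1) | Received idursulfase-IT; no later sentence overrides this | No |
| Categories 10-11 (SAP 6.8.1, general sentence) | Received idursulfase-IT | No |
| Categories 10-11 (SAP 6.8.1, specific sentence) | Device implanted | Yes |
| Device and procedure analyses (SAP 6.2, Protocol 10.4.1) | Implant procedure performed | Yes |
| Device and procedure events (Protocol 10.7.2) | Treated and device implanted | No, if treated means dosed |
| Device performance (SAP 6.8.6.7) | Implanted patients in the Safety Population | Yes |
| Substudy Population (SAP 6.2, Protocol 10.4.1) | Enrolled and dosed | No |

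The substudy has no second set to catch him. The Safety Population consists of randomized patients, and substudy patients are not randomized (Protocol 6.4). The device performance analyses are defined within the Safety Population.

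**Illustration for category 9.** Assumptions, not in the documents: all 32 planned IT-arm patients (SAP 4.1) are implanted, k of them are never dosed, each of those k has a surgery-related event, and x other patients have a regimen-related event. The dosed-only proportion is x/(32 − k). The proportion among those implanted or dosed is (x + k)/32.

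- k = 1, x = 0: 0/31 = 0.0% against 1/32 = 3.1%.
- k = 1, x = 4: 4/31 = 12.9% against 5/32 = 15.6%.
- k = 3, x = 4: 4/29 = 13.8% against 7/32 = 21.9%.

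**Chance that such a patient occurs.** If each implanted patient has probability p of never being dosed, the chance of at least one among 32 is 1 − (1 − p)^32. For p = 1%, 2%, 5% and 10% this is 0.28, 0.48, 0.81 and 0.97. The documents give no value of p.

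**The case against.** The strongest reply is that little is lost in the pivotal study, and most of that reply stands.

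- The Safety Population has no dosing condition. Pre-dose surgical events count as treatment-emergent, and the full set is used for categories 1-7, with categories 3-6 also listed. A serious surgical event is therefore reported.
- SAP 6.8.1 plans a further table of treatment-emergent events by relationship, including relationship to the IT regimen, and that sentence carries no dosed-only condition. The patient is therefore not clearly absent from every regimen-related output.
- For categories 10-11 the specific sentence follows the general one and does not require dosing. On a natural reading it governs, which leaves a drafting inconsistency.
- Loss of access through the device need not prevent dosing: lumbar puncture is allowed up to 12 times (Protocol 4.1.1). Some US patients were dosed that way before a delayed implantation (Protocol 8.3.1), so surgery did not come first for everyone.
- Substudy safety output is listings, and SAP 6.8 refers to substudy safety data without naming a set. The table shells are separate documents and might be broader.

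Three points survive. Category 9 has no sentence that lifts its dosing condition. The one defined substudy set requires dosing, and a broader listing is possible but not stated. Lumbar puncture deals with access; it does not cover a patient withdrawn for an intolerable adverse event, a newly met exclusion criterion or withdrawn consent (Protocol 7.17).

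**Conclusion.** The point holds for two stated sets and one inconsistency. The Substudy Population and the category 9 set require a dose, which conflicts with the SAP's own treatment-emergent start at surgery or first dose. The set for categories 10-11 is described in ways that disagree for undosed patients.

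A reader might go further in three directions that the documents do not support:

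- *That the pivotal Safety Population is conditioned on dosing.* It is not; SAP 6.2 requires only randomization and a safety assessment.
- *That device and surgery event rates are biased downward.* On the specific sentence in SAP 6.8.1, and on SAP 6.2, implanted but undosed patients are counted in them. The substudy has listings, so it has no rate to bias.
- *That analysis by treatment received would put an operated IT-arm patient among the controls and raise control rates.* Nothing says so. The SAP counts the device and its surgery as parts of the IT regimen and dates the IT group's window from implantation if that is earlier.

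The size is probably very small and rests on an assumed count. One pivotal patient moves category 9 from 1/32 to 0/31 in the simplest case. If the substudy enrolled 5 to 10 children (an assumption; there is no target), one omitted child would be 10-20% of them (1/10 to 1/5). Efficacy conclusions are unaffected. The rules are still worth correcting because, followed literally, they can omit a regimen harm because of the harm itself.

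**What to change.** 1. SAP 6.8.1: present category 9, overall and by SOC/PT, for patients with IDDD implant surgery or a first dose, whichever is earlier, to match the treatment-emergent start.
2. SAP 6.2 and Protocol 10.4.1: define the substudy safety set in the same way.
3. SAP 6.8.1 and Protocol 10.7.2: use the set already in SAP 6.2 and Protocol 10.4.1 (implant procedure performed) for categories 10-11, and remove the competing descriptions.
4. Keep categories 8 and 12 for dosed patients, since they concern the drug and its administration.

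The cost is a few sentences in each document and one population flag. No new data are needed, because implantation and dosing dates are already collected.
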